8. INTERVENTION DISCONTINUATION

Discontinuation of intervention for a participant: Subject may stop their participation for any reason, e.g., the subject is non-compliant with the protocol; subject develops unacceptable side effects; or psychosocial circumstances prevent continuation.

Possible reasons for discontinuation of the whole study: Study closure by NC TraCS; research environment is no longer supportive; multiple Unexpected Problems (UP); insufficient recruitment to answer research hypotheses. If greater than 3 enrolled and randomized subjects develop a grade 3 or greater adverse event due to the intervention, the entire study would be stopped and the safety monitors would reevaluate.

Early discontinuation: Participants will continue to be followed, with their permission, for another 6 weeks if study interventions are discontinued for reasons other than the normal end of the study.

Normal end to the study: Subjects completing the final evaluation will be followed up one week after the final visit by phone call to solicit any possible AEs.

9. STATISTICAL CONSIDERATIONS

9.1: General Design Issues

Primary Outcome

90-90 Knee Extension Angle Test. KEA is a functional test designed to assess lower extremity flexibility and is considered the gold standard test for assessing hamstring length (53). Results will be recorded as degrees of knee flexion angle. A clinically significant effect size is an increase of 5 degrees.

Secondary Outcomes

Handheld Dynamometry. HHD is currently considered a reliable and valid measurement of peak muscle contraction. The subject will be prone on the table with right leg bent to 90° and will maximally contract the hamstring muscle for 4-5 seconds against the HHD device. The investigator will record the mean value of three attempts.

Pain Pressure Threshold. PPT is a reliable, accurate and valid method for measuring muscle pain sensitivity and response to treatment(54). In order to determine PPT, the researcher will apply the tip of the algometer to a tender spot in the participant's hamstrings and increase the amount of pressure until the participant verbally informs the researcher when the sensation of pressure became pain. At this point the algometer is removed and the peak force recorded. The mean of three repeated measures will be reported. An increase in PPT signifies an increase in pain tolerance.

Additional Variables

Age, gender, activity level, perceived hamstring tightness, perceived hamstring flexibility and perceived hamstring strength will be assessed at baseline and subsequent follow up visit.

9.2: Sample Size and Randomization

Sample Size and Power: Based on previously published results(55), we would consider a mean increase of 5° on the KEA (e.g., from 135° to 140°) to be clinically meaningful, and we assume a common standard deviation of 15°. We further assume that correlation between repeated measurements from the same individual will be at least 0.75 (likely a conservative assumption). Under these assumptions, enrolling 38 participants would provide at least 80% power using a two-sided test at the 0.05 level. Allowing for up to 10% loss to follow-up, we will enroll 44 participants.

9.3: Definition of Populations

We are defining our intention-to-treat population as all subjects who are randomized. We will retain randomized subjects into the treatment periods to which they were assigned. For a per-protocol analysis (if necessary), we will analyze data from subjects who attend and complete both study visits.

9.4: Interim Analyses and Stopping Rules

We are not planning any pre-specified interim analyses for any reason. The study may be suspended by our PI or the Data and Safety Monitoring Committee (DSMC) if a severe adverse event occurs that is deemed to be secondary to the intervention. The DSMC may also suspend or stop the study or a study arm if reported adverse events are increasing, either across intervention arms or in a particular study arm.

9.5: Outcomes

Outcomes include two functional measures that will be logged into REDCap at the time of the evaluation. The study coordinator will verify complete data entry after each study visit.

9.5.1: Primary Outcome

We define the primary outcome as the change in angle of the KEA test from the time before to the intervention to afterwards.

9.5.2: Secondary Outcomes

We define the secondary outcome as the difference in peak hamstring strength on HHD, and difference in PPT scores between pre and post-intervention time periods.

Subgroup analyses: conduct analyses on the primary outcome stratifying on gender and baseline hamstring subjective tightness, flexibility and strength, number of prior hamstring injuries.

9.6: Data Analyses

To compare mean KEA response between treatment conditions, we will use a linear mixed effect model. The model will include fixed effects for treatment, period, and baseline pre-intervention KEA within each period. The model will include random subject effects to account for correlation between repeated measurements. Given the length of the washout period relative to the treatment period, the primary analysis will assume no carry-over effects and will estimate effect size along with a 95% confidence interval. As a secondary analysis to explore the potential for carry-over, we will include and test a fixed effect for treatment-by-period interaction. If significant carry-over is identified, we will also report comparisons using only the period 1 data. We will use a similar approach to explore intervention effects on HHD and PPT.

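### The 80% power at n=38 in section 9.2 fits a paired t-test; the section 9.6 mixed model gives about 65% at the plan's own correlation floor

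*Combined protocol and SAP*

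**What the plan says.** Section 9.2 (Sample Size and Randomization) takes as clinically meaningful "a mean increase of 5° on the KEA (e.g., from 135° to 140"°). On spread it says "we assume a common standard deviation of 15"°. On dependence it assumes that the "correlation between repeated measurements from the same individual will be at least 0.75", and it describes this as probably cautious. It then states: "Under these assumptions, enrolling 38 participants would provide at least 80% power using a two-sided test at the 0.05 level". It does not name the test behind that figure, and it does not separate readings taken within one visit from readings taken a week apart. Section 4.3 relies on the same 38 completers as enough for Aim 1.

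The outcome and analysis are defined elsewhere. Section 9.5.1: "We define the primary outcome as the change in angle of the KEA test", from before to after the intervention. Section 9.6: "The model will include fixed effects for treatment, period, and baseline pre-intervention KEA within each period", together with a random effect for subject. Section 9.6 applies a similar approach to strength (HHD) and pain threshold (PPT).

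**The concern.** Each participant contributes four KEA values: pre and post at each of two visits. A power figure for the 9.6 model needs the correlation within a visit and the correlation between visits, but 9.2 gives one number for both. The form of the model also matters. It has a single baseline coefficient next to a random subject effect, and that coefficient has to describe two relations. One is between people: flexible people are flexible before and after. The other is within a person: whether a higher baseline at one visit than at the other predicts a higher post value at that visit. The treatment comparison in a crossover is within-person. If the two slopes differ, a coefficient pulled toward the between-person slope adds baseline noise to the treatment contrast.

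At about 65% power, a true 5° difference would be missed in roughly one trial in three. The plan implies one in five.

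**Working it through.** **Inputs.** From 9.2: difference 5°, SD 15°, correlation 0.75 at the floor, two-sided 0.05, n=38 (44 enrolled). Assumed: 19 participants per sequence, no dropout within the analysed n, no carry-over (as 9.6 assumes). Write rw for the pre/post correlation within a visit and rb for every correlation between visits.

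**Step 1: reproduce the plan's figure.** For one KEA value per condition, the SD of the paired difference is 15 × √(2 × (1 − 0.75)) = 10.61°. A noncentral t calculation gives 80.8% at n=38 and 79.7% at n=37. So 38 is the smallest n that reaches 80% for this test, with 5° used as the difference between conditions.

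**Step 2: the two baseline slopes in the 9.6 model.**
- Within subject: w = (rw − rb)/(1 − rb) = (0.75 − 0.75)/0.25 = 0
- Between subjects: (rw + rb)/(1 + rb) = 1.50/1.75 = 0.857

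In REML simulation of the 9.6 model (20,000 trials, n=38) the single fitted coefficient averages b = 0.713.

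**Step 3: effect on the treatment contrast.** The contrast is in effect the post difference minus b times the pre difference. Relative to the paired difference of Step 1, its variance is multiplied by 1 − 2bw + b². At the floor this is 1 + 0.713² = 1.508, so the SD is 10.61 × √1.508 = 13.0° and the standard error is 13.0/√38 = 2.11°. The simulated standard error is 2.12–2.13°, against 1.77° when the two slopes are separated.

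**Step 4: power at the floor (rw = rb = 0.75).**
- 9.6 model, n=38: 63–67%, depending on the run and on a t or z reference. A check of 400 trials in standard mixed-model software gave 66%.
- 9.6 model, n=44: 70–72%.
- Subject-mean baseline added: 79–80% at n=38 and 84–86% at n=44.
- Type I error of the 9.6 model: 5.1–5.9%, depending on the reference distribution.

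**Step 5: dependence on the within-visit correlation (n=38, rb = 0.75).**

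| rw | w | fitted b | 1 − 2bw + b² | 9.6 model | with subject mean |
|---|---|---|---|---|---|
| 0.75 | 0 | 0.713 | 1.51 | 63–67% | 79–80% |
| 0.80 | 0.2 | 0.776 | 1.29 | 71–74% | 80–82% |
| 0.85 | 0.4 | 0.837 | 1.03 | 80–82% | 86–87% |
| 0.90 | 0.6 | 0.893 | 0.73 | 91–93% | 94–95% |

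Around rw = 0.85 the variance multiplier is close to 1, which is why power returns to about 80% there. If all correlations rise together, the 9.6 model gives about 70–74% at 0.80 and 80–84% at 0.85.

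**Step 6: a pattern in which the change gains nothing.** Suppose the within-visit, pre-pre and post-post correlations are 0.75 and the pre-post correlation across visits is 0.60. The slopes are then (0.75 − 0.60)/0.25 = 0.60 within and (0.75 + 0.60)/1.75 = 0.77 between. They lie close together, and simulated power is 93–94% for the 9.6 model and 93% with the subject mean.

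**The case against.** The strongest reply is that 65% is a boundary case. It needs a pre/post pair, taken in one visit around a 30-second treatment, to agree no better than readings a week apart. Each KEA value is also the mean of three attempts (section 3), the plan calls its correlation assumption probably cautious, and 0.75 could be meant only as the between-condition correlation. This stands in part: the shortfall is conditional and disappears at a within-visit correlation of about 0.85. It does not rescue the sentence in 9.2, which promises at least 80% for any correlation of at least 0.75. If 0.75 covers only the between-condition pair, the within-visit value is unstated and power could lie anywhere in the table.

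A second reply is that this is a pilot with a valid analysis. That also stands, and it limits the weight of the point. Still, the protocol makes a formal power claim for Aim 1 and sets enrolment by it.

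Three stronger readings are tempting but not supported:
- **That power is 52%.** This is the result for an unadjusted comparison of pre-to-post changes (SD 15 × √(4 × 0.25) = 15°). Section 9.5.1 defines a change, but 9.6 adjusts for the period baseline. With that covariate in the model, using the change or the post value as the response gives the same treatment estimate. No section plans the unadjusted comparison.
- **That the trial is underpowered.** The documents do not give the correlations that would decide this.
- **That 5° was wrongly taken from a pre-post rise.** The 135° to 140° example can be read that way, but n=38 reproduces exactly with 5° as the difference between conditions. The wording needs clarifying; no error is shown.

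**Conclusion.** The point holds as a mismatch between the power statement and the planned model, with an avoidable loss of efficiency at the floor. The stated 80% belongs to a paired t-test that 9.6 does not plan. At the floor the planned model falls short by roughly 13 to 17 percentage points at n=38, and remains at 70–72% even if all 44 participants complete. The size rests on the assumption that all four values correlate 0.75, which is the literal reading of 9.2 at its minimum. It shrinks to nothing near a within-visit correlation of 0.85.

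The planned estimate is not biased under the no-carry-over assumption, and its Type I error is close to 5%. This should be fixed before the data are examined, but it does not invalidate the analysis.

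**What to change.** **Section 9.6.** Add the subject's mean of the two pre-intervention KEA values as a second covariate beside the period-specific baseline, so that the within- and between-subject slopes are estimated separately. Do the same for HHD and PPT. The values are already collected. The cost is one degree of freedom and no extra participants. At the floor, power becomes about 79% at n=38 and 85% at n=44. Under some other correlation patterns there is little or no gain. A paired analysis of post values alone also gives about 81% at the floor, but it stays there as within-visit correlation rises (81% at 0.90, against 94–95% with the added covariate).

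**Section 9.2.** State that 5° is the CLRT-minus-sham difference, name the model behind the power figure, and give power as a range over stated within-visit and between-visit correlations. If the model is left unchanged, say that power at the floor is about 65% (n=38) or 70% (n=44), rising at n=38 to about 80% at a within-visit correlation of 0.85. Bring the sentence on adequate power in 4.3 into line. This is one rewritten paragraph, and the model change should be pre-specified before any outcome data are seen.

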Appendix B(b): Hamstring History (version 1.0)

Hamstring History Form

CLRT Hamstring Study

Please circle YES or NO in response to the following questions:

YES	NO	Have you had an injury to either leg that has altered your function in the past 6 months?
YES	NO	Have you ever had a surgery to either leg (hamstring, knee, ankle, hip)?
YES	NO	Do you have any disc or nerve injuries in your legs or lower back?
YES	NO	Do you have any known muscular abnormalities?
YES	NO	Do you have a heart condition that would stop you from exercising?

The following questions ask about previous injuries to your LEFT and RIGHT hamstring muscles:

Number of previous acute strains in your LEFT SIDE HAMSTRINGS: _____

If you answered "0" above, skip the next 3 questions regarding the left hamstring and continue at the next section.

Please circle the best answer to each question (LEFT side only):

How long ago was your most recent LEFT hamstring injury?	0-6 mo.	6-12 mo.	1-2 yr.	> 2 yr.
How long did it affect your ability to perform your normal activities?	1-3 days	4-7 days	1-4 wk.	> 4 wk.
How much has it affected your activities of daily living?	Not at all	A little	Somewhat	A lot

Number of previous acute strains in your RIGHT SIDE HAMSTRINGS: _____

If you answered "0" above, skip the next 3 questions regarding the right hamstring and continue at the next section.

Please circle the best answer to each question (RIGHT side only):

How long ago was your most recent RIGHT hamstring injury?	0-6 mo.	6-12 mo.	1-2 yr.	> 2 yr.
How long did it affect your ability to perform your normal activities?	1-3 days	4-7 days	1-4 wk.	> 4 wk.
How much has it affected your activities of daily living?	Not at all	A little	Somewhat	A lot

Please rate the following based on the scale below, ON AVERAGE:

How tight would you say your hamstrings are?	Not at all	A little	Somewhat	Very	Extremely
How strong would you say your hamstrings are?	Not at all	A little	Somewhat	Very	Extremely
How much does hamstring pain/soreness affect you?	Not at all	A little	Somewhat	Very	Extremely

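### The subgroup plan stratifies on five factors with no treatment-by-factor interaction, so it never tests whether the effect of CLRT differs between subgroups

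*Combined protocol and SAP*

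**What the plan says.** The subgroup plan is a single line in section 9.5.2: "conduct analyses on the primary outcome stratifying on gender and baseline hamstring subjective tightness, flexibility and strength, number of prior hamstring injuries". It gives no cut-points, no test of heterogeneity, no multiplicity rule and no exploratory label.

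For the main comparison, section 9.6 states that "we will use a linear mixed effect model". Its terms are listed: "The model will include fixed effects for treatment, period, and baseline pre-intervention KEA within each period", plus random subject effects. The only interaction concerns carry-over: "we will include and test a fixed effect for treatment-by-period interaction". No subgroup factor enters the model.

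The Hamstring History form (Appendix B(b)) rates tightness, strength and pain/soreness on five verbal levels. It has no item on perceived flexibility, although sections 9.1 and 9.5.2 both name that variable. Strains are counted separately by leg, including "Number of previous acute strains in your RIGHT SIDE HAMSTRINGS". Section 3 specifies that the right leg is the one tested.

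**The concern.** A subgroup analysis should ask whether the treatment effect differs between levels of a factor. Estimating or testing the effect separately in each level does not answer that. When a trial is powered at about 80% on its full sample, each half is underpowered, so one half will often reach significance and the other miss it even if the effect is identical in both. The result could be reported as CLRT working in one sex, or in people with tight hamstrings, and not in others.

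The five-level ratings and the strain count also have no stated grouping, so the strata could be formed after the data are seen. At stake is the interpretation of a subsidiary analysis in a small trial. The primary estimate does not depend on it.

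**Working it through.** **Inputs, all from section 9.2.** Effect: "we would consider a mean increase of 5° on the KEA (e.g., from 135° to 140°) to be clinically meaningful". Spread: "we assume a common standard deviation of 15" degrees. Dependence: "correlation between repeated measurements from the same individual will be at least 0.75". The test is two-sided at 0.05, with 38 evaluable subjects. Stratum sizes are not in the documents, so the splits below are assumptions.

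**Step 1: reproduce the plan's figure.** Each subject gives one within-subject treatment difference, with SD = 15 × √(2 × (1 − 0.75)) = 10.61°. For n = 38 the noncentrality is 5 / (10.61/√38) = 2.91, and the noncentral t gives 80.8% power. The stated 38 reproduces.

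**Step 2: a uniform 5° effect, two strata of one factor.** With stratum powers p₁ and p₂, the probability that exactly one is significant is p₁(1 − p₂) + p₂(1 − p₁).

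| Split of 38 | Power in each stratum (correlation 0.75) | Exactly one significant, correlation 0.75 | Exactly one significant, correlation 0.90 |
|---|---|---|---|
| 19/19 | 49% / 49% | 50% | 23% |
| 28/10 | 67% / 27% | 58% | 45% |
| 30/8 | 70% / 21% | 62% | 55% |

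For 19/19 at correlation 0.75: 2 × 0.494 × 0.506 = 0.50. At intermediate correlations the 19/19 figure is 49% (0.80) and 41% (0.85).

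**Step 3: the interaction test on the same data.** This compares mean within-subject differences between the two strata. Under a uniform effect it is significant 5% of the time per factor, whatever the split or correlation.

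**Step 4: no effect anywhere, five factors.** Simulating five random 19/19 splits of the same 38 subjects (20,000 runs), at least one of the ten strata reaches p<0.05 in about 29% of trials. At least one of the five interactions does so in about 22%. A repeat run with another seed gave 30% and 23%.

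**Step 5: what an interaction can show.** At 19/19 and correlation 0.75, the standard error of the difference between strata is 10.61 × √(2/19) = 3.44°. With t(36) = 2.03 the 95% CI half-width is 2.03 × 3.44 ≈ 7.0°. Power is about 29% for a true difference of 5° and about 81% for 10°.

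**The case against.** The strongest reply is that the line in 9.5.2 is brief rather than wrong. Stratifying could mean stratum estimates with confidence intervals, or a stratified model with a heterogeneity test. A reader might infer that the plan will declare effect modification by comparing p-values between strata. The documents do not say so: they state no within-stratum test and no decision rule, and 9.6 speaks of effect sizes with 95% intervals. This part stands, so the claim is limited to what the results could be taken to mean. It does not remove the gap, because 9.6 names an interaction where one is intended, and none is named for the subgroups.

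The 0.75 correlation is a floor that the plan itself calls conservative, and the paired calculation ignores the baseline KEA covariate, whose effect on residual SD is not given. Both points are fair. Even so, at 0.90 the discordance is still 23% to 55%.

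Low interaction power is also a fair point: a non-significant interaction would rule out little. That is a reason to report the interval, which shows how little is known.

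Three further inferences are tempting but not supported:

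- **Next trial.** No document says that the subgroup results will select a later trial's population.
- **False positives.** Treating ten strata as independent gives 1 − 0.95¹⁰ = 40% under no effect. The factors re-split the same subjects, so the figure is about 29%. Part of its excess over 22% reflects ten tests against five.
- **Both legs.** Recording strains in both legs is not a data defect. The right-leg count is available; 9.5.2 only fails to say which count it uses.

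**Conclusion.** The concern holds as a gap in the subgroup method and should be corrected. As planned, the analysis gives stratum-by-stratum results that cannot show whether the effect differs. Under the plan's inputs, a uniform effect would look split between two strata in 50% to 62% of trials per factor, and in 23% to 55% if the correlation is 0.90, against 5% for an interaction test. These figures rest on assumed two-way splits of 38 subjects and on a paired-t approximation to the mixed model. The sample size and the primary comparison are not affected.

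**What to change.** In section 9.5.2, replace the stratified analyses with one treatment-by-factor interaction per factor. Add each, together with the factor's main effect, to the 9.6 mixed model fitted to all subjects. Specify that:

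- the five-level tightness and strength ratings enter as ordered linear scores;
- prior injury is the right-leg strain count, matching the leg tested;
- the source of perceived flexibility is named, or the factor is dropped, since the Hamstring History form has no such item;
- each interaction is reported as an estimate with its 95% CI;
- stratum estimates are descriptive, without p-values, and all subgroup results are labelled exploratory.

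The cost is wording, with no extra subjects or visits; keeping perceived flexibility would mean adding an item if no other source exists. The downsides are the linear-trend assumption for the ordinal ratings and the low interaction power shown in Step 5, which the intervals would make visible.

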5. STUDY INTERVENTION

5.1: Intervention, Administration, and Duration

CLRT is a complementary or alternative intervention that incorporates principles of laser acupuncture with chiropractic cranial reflexology. Instead of acupuncture points derived from TCM, CLRT involves low level laser stimulation of two distinct cranial microsystems discovered by chiropractors. The first map of cranial reflex points/pathways (CRP) was originally discovered by a doctor named Jack Elvidge using Applied Kinesiology, and each CRP corresponds to a major muscle or group. These soft-tissue CRPs are either points or directional lines on the skull, and they appear to have an influence on the particular muscle's tonus and strength. It was originally found that stimulating a linear reflex with digital pressure in one direction relaxed the muscle's tone, and stimulating it in the opposite direction increased the tonicity.

The second set of CRPs used in CLRT were discovered by David Denton, D.C., and consists of points that relate to each vertebra of the spine, rib, sacroiliac joint, sacrum and coccyx. Denton found that subtle manipulations of these points affected the position and function of misaligned vertebra in manner similar to adjusting them directly. [name] developed CLRT after postulating that the CRP's had similar optical properties to the acupuncture meridians, and would respond to coherent light in a similar manner. Upon clinical experimentation, he found that the cranial reflexes were in fact extremely responsive to low doses of laser light. The major goal of CLRT is to quickly decrease in pain, increase joint range of motion, and achieve lasting functional improvements. CLRT can be performed with a range of laser powers from 5milliwatts (mW) to 500mW with similar results, and wavelengths from 405nm-840nm have been used successfully.

The first visit will last approximately 1 hour and the second visit will take 30 minutes.

5.2: Concomitant Interventions

5.2.1: Allowed Interventions

Subjects will be allowed to partake in their usual exercise and physical activities.

5.2.2: Required Interventions

Participation in both study arms of the crossover trial.

5.2.3: Prohibited Interventions

None.

5.3: Adherence Assessment

We will define study adherence as completion of both study visits.

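### The only planned carry-over check has almost no power for a shift that lasts the week, and its significance trigger selects chance findings for the period-1 report

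*Combined protocol and SAP*

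**What the plan says.** The Section 9.6 mixed model for KEA has fixed effects for treatment, period and the pre-intervention KEA of each period, plus a random subject effect. The primary analysis assumes no carry-over, on the ground that the washout is long relative to the treatment period. As a secondary analysis, "we will include and test a fixed effect for treatment-by-period interaction". The follow-on rule is: "If significant carry-over is identified, we will also report comparisons using only the period 1 data". HHD and PPT are to be handled in a similar way.

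The plan gives no significance level for the carry-over test, no form for the period-1 comparison, and no comparison of visit-2 baselines between the two sequences. Section 6.2.4 shows that KEA, HHD and PPT are all measured before the intervention at visit 2. The Précis sets a one-week washout. Section 5.1 lists among the general goals of CLRT to "achieve lasting functional improvements".

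**The concern.** In a two-period, two-sequence crossover, the treatment-by-period interaction is the same contrast as the difference between sequences. It is tested between subjects and gains nothing from within-subject pairing. If CLRT at visit 1 leaves a shift that is still there a week later, that shift sits in the visit-2 baseline as well as in the visit-2 post-intervention value. The baseline covariate then removes most of it before the interaction is tested. A non-significant interaction would say little about whether the effect lasted the week, yet it could be read as support for the no-carry-over assumption.

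The follow-on rule has a separate problem. The sequence contrast and the period-1 contrast share the period-1 data. Trials in which the first is significant by chance are therefore trials in which the second tends to be extreme. Reporting period 1 only in those trials puts a selected estimate beside the primary result.

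**Working it through.** **Inputs.** From Section 9.2: "enrolling 38 participants would provide at least 80% power using a two-sided test at the 0.05 level"; a 5° effect; "to be clinically meaningful, and we assume a common standard deviation of 15"°; "correlation between repeated measurements from the same individual will be at least 0.75". From Section 9.6: the model terms. Assumed because the plan does not say: a 0.05 trigger, a period-1 ANCOVA on the visit-1 baseline, and correlation 0.75 between all four KEA readings (with higher within-visit correlations as sensitivity).

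**1. The plan's own figure reproduces.** SD of the within-subject difference = 15 × √(2 × (1 − 0.75)) = 10.61. Normal approximation: (10.61 × (1.960 + 0.842) / 5)² = 35.3, so 36. With the noncentral t, 38 participants give 80.8% power (paired) or 80.7% (crossover), and 37 give under 80%. The plan adds: "Allowing for up to 10% loss to follow-up, we will enroll 44 participants". 38 / 0.90 = 42.2, so 43, and 44 covers it.

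**2. How much of a lasting shift reaches the interaction.** Simulating the Section 9.6 model gives a fitted baseline slope of about 0.71 at correlation 0.75, 0.89 at within-visit correlation 0.90 and 0.945 at 0.95. The baseline therefore removes about 71–95% of the shift. The shift affects one of the two periods in the CLRT-first sequence, so the expected interaction estimate is (1 − slope) × shift / 2:
- 5° shift: (1 − 0.708) × 5 / 2 = 0.73° (simulated 0.74°)
- 10° shift: (1 − 0.708) × 10 / 2 = 1.46° (simulated 1.48°)

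**3. Its standard error.** Residual SD given baseline = 15 × √(1 − 0.75²) = 9.92. SE of a one-period contrast with 38 participants = 9.92 × √(4/38) = 3.22°. The fitted residual correlation between periods is 0.161, so the two-period sequence contrast has SE 3.22 × √(1.161/2) = 2.45°. The signals in step 2 are thus about 0.30 and 0.60 standard errors.

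**4. Rejection rates (n = 38, SD 15°, correlation 0.75, two-sided 0.05).** Hand values use the normal approximation. The simulation column gives the range over separate runs.

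| Test and carry-over | Signal / SE | By hand | Simulated |
|---|---|---|---|
| Interaction, lasting 5° | 0.73 / 2.45 | 6% | 4.6–5.6% |
| Interaction, lasting 10° | 1.46 / 2.45 | 9% | 7.0–8.2% |
| Interaction, 5° in visit-2 response only | 2.5 / 2.45 | 17% | 16–17% |
| Interaction, 10° in visit-2 response only | 5 / 2.45 | 53% | 50–51% |
| Visit-2 baseline ANCOVA, lasting 5° | 5 / 3.22 | 34% | 31–32% |
| Visit-2 baseline ANCOVA, lasting 10° | 10 / 3.22 | 87% | 84–85% |

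Under the null the interaction rejects in 4.8% of trials. At within-visit correlation 0.90 it rejects in 4.6% (5°) and 5.5% (10°) for a lasting shift. The covariate is not the only cause: without it, a sequence test rejects in only 8% and 18%. The baseline ANCOVA's power for a lasting 5° shift rises to 47% at between-visit correlation 0.85 and about 63% at 0.90. For carry-over confined to the visit-2 response it rejects in only 4–5%, its null rate.

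**5. The trigger, with no treatment effect and no carry-over.** If the residuals of the two periods were independent, the sequence and period-1 contrasts would correlate √(1/2) = 0.707, and the bivariate normal gives 34% for period-1 p<0.05 given interaction p<0.05. Simulation gives 36–38% at correlation 0.75 and 32–37% at within-visit 0.90. Other assumptions give about 25–50%: 28% with a 0.10 trigger, 25–37% with a change-score test, 47–50% if individual response is stable across visits. The unconditional period-1 rate is 4.9–5.0%. Jointly: 0.048 × 0.384 = 1.8% of null trials. At correlation 0.75 the mean absolute period-1 estimate is 5.4° when the trigger fires, against 2.6° overall. At within-visit 0.90 the triggered mean is 3.7°.

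**6. Effect on the primary estimate (true effect 5°).** The bias is minus the share of the shift that escapes the baseline, halved.
- Lasting 5° shift: 5 − 0.73 ≈ 4.3°, rising to 4.9° at within-visit correlation 0.95.
- Lasting 10° shift: about 3.6° (simulated, correlation 0.75).
- Visit-2 response only: 5 − 5/2 = 2.5° for a 5° carry-over, and 5 − 10/2 = 0° for 10°.

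**The case against.** The strongest reply is that the form of carry-over the test misses does little damage. The same baseline adjustment that hides a lasting shift protects the treatment estimate, and the remaining bias is toward zero. The damaging form is one that changes only the visit-2 response, and there the planned interaction has some power (about 17% and 50%) while a visit-2 baseline comparison has none. This stands. It means the interaction should not be dropped in favour of the baseline comparison, and that the check is not uninformative about every kind of carry-over.

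It is also fair that the classical two-stage procedure replaces the crossover result with period 1, whereas this plan only reports period 1 in addition, within an exploratory secondary analysis of a pilot. A reader might infer from the 38% that the trial has an inflated false-positive rate. The documents do not support that: the figure is conditional on the trigger firing under the null, the primary test is untouched, and the joint event is under 2%.

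Finally, a reader might take the Section 5.1 goal of lasting improvement as evidence that a week-long shift is expected here. It describes CLRT in general, while this trial's aims concern acute effects. It leaves the duration of effect open and does not establish carry-over. Equally, a long washout relative to a 30-second application does not show how long the effect lasts.

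**Conclusion.** The point holds with limited weight. For a shift present in both visit-2 readings, the planned test rejects at close to its nominal level (about 5–8% for 5–10°), through baseline absorption and low between-subject power together. Calling it blind to carry-over in general would go too far: 5–29% of a lasting shift still leaks through, and carry-over in the visit-2 response alone is sometimes detected. The significance trigger selects chance extremes, with a conditional false-positive rate of about 32–38% under the stated assumptions and 25–50% across others.

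The primary estimate stays in place and is only modestly biased by a lasting shift, so severity is low to moderate. The figures rest on Section 9.2's SD and correlation, 38 evaluable participants, and the assumed 0.05 trigger and baseline-adjusted period-1 test. The simulated shifts are taken as undiminished after a week. The case for changing the plan is that a direct measure of a lasting shift is already collected and goes unused.

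**What to change.** In Section 9.6:

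1. Keep the treatment-by-period interaction, but report it as an estimate with its 95% CI rather than as a pass/fail test.
2. Add a pre-specified comparison of visit-2 pre-intervention KEA between sequences, adjusted for visit-1 pre-intervention KEA, always reported with its 95% CI. Do the same for HHD and PPT.
3. Delete the significance trigger. Report the period-1 comparison either always, labelled descriptive and with its model stated, or not at all.

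The cost is SAP wording and one ANCOVA per outcome on data already collected. The added comparison has limits. At correlation 0.75 its power for a 5° shift is only about 32%, and its 95% CI would be roughly ±6.5° (2.03 × 3.22), so it should be read as an interval and not as a test. It cannot see carry-over confined to the visit-2 response, which is why the interaction estimate stays.
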